3.4. Procedures

Figure 7 (above) outlines study procedures. Once enrolled, participants will complete a baseline assessment lasting 9 days (see **Table 5**, below), and final eligibility determination will be made after the baseline assessment is complete. Women Veterans who meet all study criteria and agree to continue participation will be randomized to receive either the ABC-I program or a similarly-structured CBT-I program. Throughout treatment, adherence will be monitored, and after treatment, selected baseline measures will be repeated to measure the immediate effects of the treatments on sleep. Participants will be re-assessed 3 months later to assess maintenance of gains.

All data will be collected by trained research personnel, using participant interview, medical record review, and participant monitoring. Research staff will undergo structured training, including review of human subjects protection issues, emergency procedures, basic interviewing techniques, cultural sensitivity training, and in-depth instruction on data collection instruments and equipment. We have developed procedure manuals for all instruments and equipment to be used in this study. Adequate inter-rater reliability will be established prior to beginning the study and will be repeated on an annual basis. These procedures have resulted in consistent, reliable data collection in our prior work. The methods and instruments we have selected were chosen to minimize participant burden while maximizing reliability and validity. Assessment staff will be blinded to the intervention group to which the participant is assigned and to the study hypotheses. This blinding and separation of intervention and assessment staff will also facilitate completion of the post-treatment and follow-up assessments by participants who drop-out of the treatment. To offset expenses associated with travel and/or childcare during assessment visits, we will offer a monetary incentive for each assessment visit. Incentives will not be offered for treatment sessions as that would not be consistent with usual care.

Table 5: Screening, enrollment and baseline data collection process

	Day 1 Visit 1	Night 1	Day 2 Visit 2	Nights 2-8				Day 9 Visit 3
Informed consent; demographics	X							
WatchPAT overnight sleep apnea monitoring*	X	X	X					
Questionnaire assessments: Part 1	X							
Questionnaire assessments: Part 2			X					
Wrist actigraphy* and sleep diary			X	X	X	X	X	X

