24%	326	260	212	178	152	130	114
26%	436	336	268	218	182	154	134
28%	612	448	344	274	224	186	158

3.8d: Data analysis for Aims 2 and 3 (Hypothesis 2: ABC-I and CBT-I will be similarly effective in improving self-reported and objectively measured sleep from baseline to post-treatment; Hypothesis 3: ABC-I and CBT-I will be similarly effective in improving self-reported and objectively measured sleep from baseline to 3-months follow-up).

Two Step Hypothesis Testing of Non-inferiority: Hypotheses 2 and 3 seek to show that ABC-I is not inferior to CBT-I in terms of treatment effects (i.e., changes in sleep quality). Non-inferiority is established by framing the null

hypotheses in terms of the difference between the treatment means and comparing this difference to a pre-specified value, delta (δ), which represents the equivalence margin.

Determination of delta (δ): We elected to use a value of δ equivalent to an effect size of $d=0.40$. (i.e., 4/10ths SD). With respect to ISI, this represents a 2 point difference between the treatment effects. For PSQI, this represents a 1.4 point difference, and for actigraphically-estimated sleep percent, a difference of 5%.

Description of analysis: With respect to this study, non-inferiority is established by showing that the efficacy of ABC-I is no more than δ units less than CBT-I (**Table 12**).⁸⁸ This is tested by formulating a one sided null hypothesis that the difference between CBT-I and ABC-I is greater than or equal to δ (i.e., $H_0: \mu_{CBT-I} - \mu_{ABC-I} \geq \delta$) against the alternative hypothesis that the difference is less than δ (i.e., $H_A: \mu_{CBT-I} - \mu_{ABC-I} < \delta$). If the null

[figure not shown]
Table 12: Hypothesis testing in a non-inferiority study comparing ABC-I to CBT-I.

Type of study	Hypotheses	
	Null hypothesis (H_0)	Research Hypothesis (H_1)
Traditional comparative study	There is no difference between ABC-I and CBT-I	There is a difference between ABC-I and CBT-I
Non-inferiority study	ABC-I is inferior to CBT-I	ABC-I is not inferior to CBT-I (H₂ and H₃)

hypothesis is rejected, then the non-inferiority of ABC-I is established. For Aims 2 and 3, this two step process avoids the pitfall of erroneously interpreting a failure to reject the null hypothesis as evidence of no difference

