Hypothesis 3 will explore whether improvements seen at post-treatment are maintained over a 3-month follow-up time period. As with hypothesis 2, for each outcome measure, a 2 (group) by 3 (time) between/within analysis of variance (ANOVA) will be performed, but two interaction contrasts will be examined. The primary contrast of interest will examine impact of ABC-I (compared to CBT-I) on the change from baseline to 3 month follow-up by applying a -1 0 1 contrast to time and interacting that with treatment group. This interaction contrast will assess the impact of the ABC-I (compared to CBT-I) from baseline to the 3 month follow-up, assessing the persistence of the treatment effects. A secondary contrast will examine the change from post-treatment to six month follow-up by applying a 0 -1 1 contrast on time and interacting that with treatment group. This secondary comparison will assess differences in changes from post-treatment to 3 month follow-up for the ABC-I and CBT-I groups. Conceptually, this second contract will test whether there is either continued improvement after post-treatment (i.e., sleep is better at 3 months follow-up compared to post-treatment, or whether there is relapse (i.e., sleep is worse at 3 months follow-up compared to post-treatment).

Sample Size Calculations: For Aims 2 and 3, the required sample size was determined based on the minimum clinically-meaningful difference between the two treatments, rather than on the estimated effect size for an active treatment versus control condition. This non-traditional approach is required for comparative effectiveness designs.⁸⁸ To develop estimates of clinically-meaningful differences between treatments, we examined studies of CBT-I in the published literature.⁸⁹⁻⁹¹ We then considered clinically meaningful changes in ISI and PSQI scores and in objectively-measured sleep percent. We determined that a difference between the two treatment groups of more than 2 points on the ISI or PSQI, or more than 5% in objectively-measured sleep percent would constitute a clinically-meaningful difference between the treatments. This represents an effect size of approximately $d=0.40$ (that is, 4/10s of a standard deviation for each outcome measure). The required sample size (with alpha=.05 and .80 power) to detect for an effect size of 0.40 is n=138. We plan to randomize

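### The secondary Hypothesis 3 contrast measures differential change between arms, not relapse or continued improvement, and no time contrast is named for the maintenance question the plan states

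*Combined protocol and SAP*

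**What the plan says.** Section 3.4 (Procedures) gives the purpose of the 3-month visit: "Participants will be re-assessed 3 months later to assess maintenance of gains". In Section 3.8d, the statistical analysis text for Hypothesis 3 opens the same way: "Hypothesis 3 will explore whether improvements seen at post-treatment are maintained over a 3-month follow-up time period".

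The formal hypothesis, in the title of Section 3.8d, is comparative: "ABC-I and CBT-I will be similarly effective in improving self-reported and objectively measured sleep from baseline to 3-months follow-up".

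Each outcome is analysed with a 2 (group) by 3 (time) ANOVA, "but two interaction contrasts will be examined":

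- Primary: "applying a -1 0 1 contrast to time and interacting that with treatment group".
- Secondary: "applying a 0 -1 1 contrast on time and interacting that with treatment group".

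The plan then describes the secondary contrast twice. The first description is "This secondary comparison will assess differences in changes from post-treatment to 3 month follow-up for the ABC-I and CBT-I groups". The next sentence says that "this second contract will test whether there is either continued improvement after post-treatment" or relapse, which it explains as sleep being better or worse at 3 months than at post-treatment. (The word contract is evidently a slip for contrast.)

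The Hypothesis 2 contrast is also crossed with group. No contrast on time alone, within an arm or averaged over arms, is named, and no criterion for maintenance is given.

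**The concern.** The two consecutive descriptions give one contrast two meanings. The first is a difference between arms in their change. The second is a change over time. These are different estimands, and the formula in the plan delivers only the first.

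The stake is interpretation. An analyst who follows the second sentence would look to this contrast to learn whether gains lasted. A result near zero would be uninformative on that question, because equal maintenance, equal relapse and equal further improvement all give the same value. The primary contrast has the same property, so it does not fill the gap. The plan would then state a maintenance question without naming an estimate that answers it.

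**Working it through.** **Inputs**

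- From the plan: contrasts (-1, 0, 1) and (0, -1, 1), each crossed with group; 74 per arm (Section 3.4c); ISI margin of 2 points, equal to 0.40 SD (Section 3.8d), so the implied SD is 2 / 0.40 = 5; one-sided non-inferiority test; alpha 0.05.
- Assumed, not in the documents: ISI means of 18 at baseline and 8 at post-treatment; within-person correlation 0.5 in the simulation and 0.6 to 0.8 in the precision calculation.

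The plan gives no figure of its own to reproduce on this point.

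**Step 1: what the contrast equals.** Let the arm means be m1, m2, m3 at baseline, post-treatment and 3 months. The secondary contrast crossed with group is

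(m3 - m2) in ABC-I minus (m3 - m2) in CBT-I.

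The same contrast averaged over arms is half the sum of the two changes. Higher ISI is worse, so a positive change means relapse.

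| Scenario (ISI at post-treatment, then 3 months) | (0, -1, 1) by group | (-1, 0, 1) by group | (0, -1, 1) averaged over arms |
|---|---|---|---|
| Both maintain (8, 8) | 0 - 0 = 0 | 0 | 0 |
| Both lose 5 points (8, 13) | 5 - 5 = 0 | 0 | +5 |
| Both relapse fully (8, 18) | 10 - 10 = 0 | 0 | +10 |
| Both improve 3 more (8, 5) | -3 - (-3) = 0 | 0 | -3 |
| Only ABC-I loses 5 | 5 - 0 = 5 | 5 | +2.5 |

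The zeros are algebraic: they hold for any means, SD or correlation, provided that the arms change equally.

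**Step 2: simulated behaviour.** 3,000 trials per scenario, 74 per arm, SD 5, correlation 0.5, two-sided 0.05 for the contrasts, one-sided 0.05 non-inferiority at 3 months with margin 2.

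| Scenario | Interaction (0, -1, 1) rejects | Pooled time (0, -1, 1) rejects | Non-inferiority declared |
|---|---|---|---|
| Both maintain | 4.2% | 4.9% | 77.4% |
| Both lose 5 | 5.3% | about 100% | 78.4% |
| Both relapse fully | 5.3% | about 100% | 79.4% |
| Both improve 3 more | 5.1% | about 100% | 77.9% |
| Only ABC-I loses 5 | about 100% | about 100% | 0% |

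The interaction rejects at its nominal error rate in all four equal-change cases and detects differential relapse well. The pooled time contrast separates the equal-change cases.

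**Step 3: precision of the missing estimate.** For one arm, SE = 5 × sqrt(2(1 - r)) / sqrt(74), and the 95% half-width is 1.96 × SE.

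- r = 0.6: SE 0.52, half-width 1.02
- r = 0.7: SE 0.45, half-width 0.88
- r = 0.8: SE 0.37, half-width 0.72

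These use all 74 per arm. At the 90% follow-up that Section 3.8b reports for the team's study of older Veterans, each is multiplied by sqrt(1 / 0.90) = 1.054, giving about 0.76 to 1.07.

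**The case against.** The strongest reply is that the formal Hypothesis 3 is a comparison between arms, and the primary (-1, 0, 1) by group contrast, tested against the margin, addresses exactly that. The secondary contrast is a valid test of differential relapse, and the sentence immediately before the faulty one describes it correctly. The fitted model also contains a time effect and yields arm means at each visit, which would expose a shared relapse to any reader. On this view the fault is one loose sentence about a secondary contrast.

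Most of this stands. A reader might infer that nothing in the plan addresses Hypothesis 3. The documents do not support that, because the hypothesis as formally stated is tested. A reader might also infer that non-inferiority after equal relapse would be a false conclusion. It would be true for the stated hypothesis, and it is not certain to be reached (79% in the simulation, against 77% under full maintenance). Nor does the plan say that a null secondary result will be taken as proof of maintenance.

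What the reply does not remove is the maintenance question itself, which the plan raises in two places. The time effect is assigned no hypothesis, and an omnibus test over three levels would not isolate post-treatment versus 3 months: a large fall from baseline could make it significant whatever happened afterwards.

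Whether CBT-I works in this trial is a general limit of active-controlled non-inferiority designs and a separate matter from this contrast.

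**Conclusion.** The point holds as a misdescribed secondary contrast together with an unnamed time contrast. The (0, -1, 1) by group term estimates differential change only and is zero under any equal change in the two arms. This follows from the definition and needs no assumption. The rejection rates and half-widths do rest on assumptions: SD 5 from the plan's margin, 74 complete participants per arm, illustrative ISI means, and correlations that the documents do not give.

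It should be corrected before analysis, because the sentence as written assigns the wrong test to a stated question. Its reach is limited. Adherence and attrition, which Section 3.1 names as the primary outcomes, are untouched, as are the non-inferiority tests and the sample size.

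**What to change.** 1. From the model already planned, estimate the (0, -1, 1) time contrast in each arm and pooled over arms, with 95% confidence intervals. Base any statement about maintenance, relapse or continued improvement on these estimates.
2. Keep the group-by-time version, labelled as the between-arm comparison of change.
3. Reword the sentence that begins with Conceptually so that it refers to differential change. In the same paragraph, correct the one mention of a six-month follow-up, since the design has 3 months.
4. Optionally, show within-arm changes from baseline to post-treatment and to 3 months beside each non-inferiority result. This helps interpretation but, without an untreated control, does not prove efficacy.

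Rewording alone would remove the contradiction but leave the maintenance question without a named estimate, so step 1 is the better remedy. The cost is a few extra secondary estimates and some wording. No new data are needed.
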